8.5 Study Exit Procedures

A Study Termination form will be completed for all patients who have completed the Study Procedures according to the protocol as well as for those who are terminating early for any cause

9. Statistical Considerations

Sample size determination for primary outcome regional wall abnormalities: Our consultant, [name] has previously demonstrated a difference in this variable in 8 to 10 patients using a similar protocol to this proposal when comparing standard and biofeedback dialysis and dialysis cooling ^{33,34}. Sample size of 10 would appear to be sufficient to detect a difference of 20% and is based upon a standard deviation of 14%, significance level of 0.05 and 80% power. In the [name] studies, differences of greater than 20% were observed. We plan to recruit 10 patients in this study, to better ensure an adequate sample size to obtain statistically relevant primary and secondary endpoint comparisons. The patients will serve as their own controls, comparing BL-SHH parameters to SCD therapy parameters. Independent t-test will be used to compare the peak frequency of MS between SHH and SCD sessions. Global LVEF and wall motion in 16 segments in 8 regions at each time point in the dialysis session will be compared using repeated measures and Bonferroni's test for multiple comparisons. IDWG will be compared using paired and unpaired non-parametric testing or t-test if the variable is

normally distributed. These approaches have shown significance in prior studies for MS in HD. Statistical correlations are planned for regional wall abnormalities, inflammatory indices, monocyte subsets and pre-dialysis blood pressures ^{33,34}

10. Adverse Events

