4.2 Number of Subjects

10 Subjects will be studied in this protocol.

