8.3.1 Study Treatment

Each Subject will have the treatments described below, during which identical study procedures will be performed during each study treatment.

Treatment 1: Initial standard hemodialysis treatment with heparin (SHH) anticoagulation.

Treatment 2: A single hemodialysis treatment with SCD treatment and regional citrate anticoagulation one week after Treatment 1.

Each subject's safety data will be monitored by the PI on an ongoing basis.

Prior to start of Study Treatment (SHH or SCD Treatment)

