8.4 Detailed Study Measures

8.4.1 Echocardiographic Methods

Complete transthoracic echocardiograms including structural imaging, color Doppler for evaluation of valvular regurgitation, spectral Doppler for hemodynamic quantitation and longitudinal strain in 3 views for calculation of global longitudinal strain (GLS) will be performed at each time point as per the specified protocol.

All echocardiograms will be performed on an identical echocardiographic platform (Epiq, Philips Ultrasound, Andover MA) using identical platform upgrades and software. Standard measures of left ventricular dimensions and volume from which ejection fraction will be calculated will be

performed off-line using the digitized images. The calculation of GLS will be performed using the integrated software of the platform.

Specific echocardiographic parameters to be quantified at each time point are as noted on the echocardiographic case report form.

Because the majority of echocardiographic parameters which reflect left ventricular contractility are both pre-and afterload dependent a substantial range of findings across patients is unavoidable and it is not feasible within the scope of a study this size to identify “normative” values nor is it possible to accurately identify thresholds of change in parameters such as ventricular size or ejection fraction in patients in whom intravascular volume and systemic systolic pressures vary. Each patient will therefore serve as his or her own control comparing pre-and post-dialysis echocardiograms following standard dialysis compared to pre-and post-echocardiograms following investigational dialysis using the SCD device^{36,37}.

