Assessment: Echocardiographic parameters which are less (but not entirely) preload and afterload dependent include quantitation of regional wall motion abnormalities as well as calculation of GLS. Normative values for regional wall motion abnormalities are defined as normal thickening and endocardial excursion in all regions and any deviation from normal thickening or excursion is considered abnormal. Regional wall motion will be scored using a standard wall motion scoring scheme. (1=normal; 2=hypokinetic; 3= akinetic; 4=dyskinetic). Scores will be tabulated for each of 16 predefined segments and a global wall motion score calculated as the sum of individual scores divided by the number visualized segments. For this scheme a score of 1 represents normal ventricular function with progressively higher numbers representing progressively worse systolic function. Scores from pre HD, post HD and 24 hour post HD Echos from all 10 patients will be collated and analyzed for statistical significance between Treatment 1 and Treatment 2 groups.

Global longitudinal strain will be obtained using tissue tracking methodology³⁸. There is a significant range within the left ventricle of normal values for regional strain depending on wall location. Values for normal GLS in normal controls have ranged from -16.0 to -22.0. Patients with systemic diseases including hypertension, diabetes and renal disease have all been described to have reduced GLS in the absence of overt systolic dysfunction. As “normal” values for GLS cannot be predicted in the patient population under consideration each patient will serve as his or her own control for tracking improvement or deterioration in global longitudinal strain.

Assessment: The largest body of data regarding using global longitudinal strain for tracking myocardial performance is in the patients receiving cardiotoxic chemotherapeutic agents where a threshold of 10-15% change has been considered as significant variation from baseline³⁹. This will be used as a dichotomous threshold for defining either improvement or deterioration in GLS.

Echocardiographic images will be interpreted at the Echo Laboratory, Frankel Cardiovascular Center, Floor 3. Area B, University of Michigan, Ann Arbor, MI

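### An independent t-test is named for peak myocardial-stunning frequency, although the same 10 patients have both sessions and act as their own controls

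*Combined protocol and SAP*

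**What the plan says.** Section 9 (Statistical Considerations) describes the comparison as within-patient: "The patients will serve as their own controls, comparing BL-SHH parameters to SCD therapy parameters". The next sentence names the test for the stunning endpoint: "Independent t-test will be used to compare the peak frequency of MS between SHH and SCD sessions".

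The rest of the plan confirms that the data are paired:

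- Section 4.2: "10 Subjects will be studied in this protocol".
- Section 8.3.1 gives every subject the SHH session first, then: "Treatment 2: A single hemodialysis treatment with SCD treatment and regional citrate anticoagulation one week after Treatment 1".
- Section 8.4.1: "Each patient will therefore serve as his or her own control comparing pre-and post-dialysis echocardiograms following standard dialysis", set against the same comparison for the SCD session.

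Other endpoints are handled in three ways:

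- Soluble markers (8.4.2) and flow cytometry (8.4.3) get repeated-measures ANOVA and paired t-tests.
- In Section 9, ejection fraction and segmental wall motion at each time point get repeated measures with a Bonferroni correction. Section 8.4.1 says wall motion scores will be "analyzed for statistical significance between Treatment 1 and Treatment 2 groups" and names no test.
- For interdialytic weight gain Section 9 leaves both options open: "IDWG will be compared using paired and unpaired non-parametric testing or t-test".

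The sample-size statement, made for regional wall abnormalities, reads "Sample size of 10 would appear to be sufficient to detect a difference of 20% and is based upon a standard deviation of 14" per cent, with a 0.05 significance level and 80% power. It does not say whether 14% is the SD within a session or the SD of the within-patient differences.

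**The concern.** An independent t-test is built for two unrelated groups, and this trial has one. When each patient supplies a value to both sessions, the variance of the mean difference depends on rho. The independent test fixes rho at zero, so its p-value and confidence interval are right only in that case.

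The own-control design exists to remove between-patient variation, and this test puts that variation back. A patient prone to stunning in one session is likely to be prone to it a week later, so rho is probably positive and the test conservative. What is at stake is a real effect missed, or an effect estimated too loosely, in a 10-patient pilot. The endpoint is also the one closest to the stated aim of reducing stunning events, while the exploratory biomarkers already get a paired analysis.

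**Working it through.** **Inputs from the documents.** n = 10 patients, each with both sessions (4.2, 8.3.1); difference 20%, SD 14%, significance level 0.05, power 80% (Section 9).

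**Assumptions.** Two-sided test; normal data; 20% means absolute points; the 20% and 14% given for regional wall abnormalities also apply to peak MS frequency, which is not defined. Rho is not given, so a range is shown.

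**Step 1: the plan's sample size.** Patients needed for 80% power at 20 points (noncentral t):

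- Independent test, SD 14 per session: 8.76, so 9 per session. Power with 10 is 85.5%.
- Paired test, SD 14 per session, rho 0: SD of differences = 14 × √2 = 19.8. This needs 9.78, so 10. Power with 10 is 81.1%.
- Paired test, SD of differences 14: 6.03, so 7. Power with 10 is 97.9%.

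Ten patients are therefore sufficient under each reading, including for the paired test.

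**Step 2: what the independent test gets wrong.** With per-session SD σ, the true variance of the mean difference is 2σ²(1 − ρ)/n. The independent test estimates 2σ²/n, so its standard error is too large by 1/√(1 − ρ); at rho 0.5 that is 1.41. It uses t on 18 degrees of freedom (2.101) where the paired test uses 9 (2.262), which gives back a factor of 0.93. The net width ratio is about 1.41 × 0.93 = 1.31; simulated mean widths give 1.3.

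Simulation, 400,000 trials per cell, n = 10. These results do not depend on the 20% or 14%:

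| rho | True type I error, independent test | 95% interval width, independent ÷ paired |
|---|---|---|
| 0 | 5.0% | 0.94 |
| 0.3 | 2.2% | 1.1 |
| 0.5 | 1.0% | 1.3 |
| 0.7 | 0.2% | 1.7 |
| 0.8 | 0.06% | 2.1 |

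The paired test stays at 5.0% throughout. At rho −0.3 the independent test's error rises to 8.4%.

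**Step 3: power at 20 points.** Reading A takes 14% as the per-session SD. Reading B takes it as the SD of differences, so the per-session SD is 14/√(2(1 − ρ)): 9.90, 11.83, 14.00, 18.07 and 22.14 at rho 0, 0.3, 0.5, 0.7 and 0.8.

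| rho | A: independent | A: paired | B: independent | B: paired |
|---|---|---|---|---|
| 0 | 86% | 81% | 99% | 98% |
| 0.3 | 89% | 92% | 97% | 98% |
| 0.5 | 92% | 98% | 92% | 98% |
| 0.7 | 95% | 99.9% | 73% | 98% |
| 0.8 | 96% | >99.9% | 49% | 98% |

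Under Reading B the independent test passes through 80% at rho about 0.65 (80.3% at 0.65, 79.0% at 0.66).

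**Step 4: a smaller effect.** Under Reading A with a true difference of 10 points, power (independent against paired) is 28% against 52% at rho 0.5, and 25% against 74% at rho 0.7.

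**The case against.** The strongest reply is that little turns on this sentence. Section 4.1 calls the trial an exploratory pilot and the synopsis calls the primary analyses descriptive. The error is conservative under positive correlation. Ejection fraction and wall motion already have a repeated-measures analysis in Section 9, so the fault lies in one undefined summary measure. The serious power loss needs Reading B with rho above about 0.65, while the stated 80% power fits Reading A better: 10 pairs give 81% at rho 0 under A, but 98% under B. The power figures also borrow an effect and an SD given for another measure.

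Most of this stands as a limit on size. None of it makes the named test correct. Section 9 still plans a significance test, and an over-wide interval harms a descriptive reading too, if one is reported. The repeated-measures sentence concerns ejection fraction and wall motion at each time point, not peak MS frequency between sessions. Reading A fits the figures better, but the wording does not exclude B. The type I error and interval-width results need neither the 20% nor the 14%.

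Two practical cautions also stand. If the measure is yes/no per session, no t-test fits. And Section 8.3.1 makes the SCD session conditional on a safety review and blood counts, so there may be fewer than 10 complete pairs; with 8, paired power at rho 0 under Reading A is 69%. Neither argues for an unpaired test.

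**Conclusion.** The concern holds. Section 9 names a test that contradicts the design stated in the sentence before it, and nothing elsewhere corrects it for this endpoint. For rho between 0.3 and 0.7, the test runs at 2.2% down to 0.2% instead of 5%, with an interval 1.1 to 1.7 times as wide as necessary. At 20 points it keeps at least 85% power for rho 0 or above under Reading A; under Reading B it drops to 73% at rho 0.7 and 49% at rho 0.8.

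The type I error and width results rest on normality, 10 complete pairs and the assumed range of rho. The power results also rest on applying the 20% and 14% to this endpoint as absolute points. The point should be fixed, but its weight is moderate: the error costs precision in an exploratory pilot and, unless rho is negative, does not produce false positives.

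**What to change.** Replace the sentence in Section 9 with:

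> *A paired t-test on the within-patient SHH minus SCD difference in peak frequency of MS (Wilcoxon signed-rank test if the differences are clearly non-normal) will be used, reported with its two-sided 95% confidence interval.*

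In the same edit:

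- Define peak MS frequency. The sentence above assumes a count or percentage.
- State which SD the 14% is, and base any restated sample size on the paired test. Ten pairs give 98% power at 20 points under Reading B, and 81% at rho 0 (more at positive rho) under Reading A.
- Say how a patient with only one session will be reported.

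The signed-rank fallback costs little. With ten untied, non-zero differences its attained level is 2 × 0.0244 = 4.9%. On normal data its power is 97% under Reading B, and 79%, 91%, 97% and 99.9% at rho 0, 0.3, 0.5 and 0.7 under Reading A. Ties, likely with a segment count, would change the attained level.

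The change needs no new data, visits or patients. If rho is exactly 0, the paired test gives up about 4 points of power under Reading A (81.1% against 85.5%) and about 1 point under Reading B. At rho −0.3 under Reading A it gives up more (70% against 83%), but there the independent test's error rate is 8.4%. Pairing does not remove any order effect, because SHH always comes first; the report should say so.

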The mortality rate in ESRD patients requiring chronic hemodialysis treatment is unacceptably high with almost half of the deaths due to cardiovascular disease (CVD). This excessive CVD mortality is not due to classical atherosclerotic disease complications but mainly due to cardiac failure and sudden death, often during the dialysis procedure^{1,2}. The pathogenesis of heart failure in this patient population appears to be due to intradialytic recurrent myocardial stunning (MS) as defined as ischemia mediated transient reduction in myocardial function. Overtime these recurrent ischemic insults results in irreversible fibrotic changes, chronic heart failure, arrhythmias, and sudden cardiac death^{3,30,31}. In this regard, hemodialysis-induced myocardial ischemia and MS has been found to be common in these patients and is significantly associated with high rates of ultrafiltration and intradialytic hypotension⁴. Of note, pediatric patients devoid of atherosclerotic coronary artery disease also have had a high incidence of MS³². MS in HD patients promotes both ischemia induced areas of hypokinesis and akinesis. The majority of these areas of MS improve within 30 minutes post hemodialysis^{33,34}. More frequent HD regimes are associated with lower UF volumes and reduction of intradialytic hypotension and MS events. This relationship may explain in part improved outcomes associated with more frequent HD, such as nocturnal or home HD, compared to the conventional 3 times a week HD treatment program³⁵. MS may be the critical pathophysiologic factor promoting the CV related deaths predominated by heart failure and sudden death in ESRD patients on chronic hemodialysis.

Immunomodulatory Biomimetic Device to Treat Myocardial Stunning in ESRD Patients

This clinical protocol will evaluate the influence of the SCD on myocardial stunning events in ESRD patients in chronic hemodialysis patients. Regional citrate anticoagulation

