4.1 Design

This is an exploratory pilot trial. The subject population to be studied are those who have been on chronic hemodialysis for ≥ 3 months with recurrent intradialytic weight gain >0.04 kg/kg body weight.

[figure not shown]
Regional myocardial wall abnormalities and biomarker measurements will be compared pre and post hemodialysis with standard heparin anticoagulated hemodialysis treatment and after one hemodialysis treatments with the regional citrate anticoagulated SCD device.

[figure not shown]
Two different treatment regimens are planned for this clinical trial.

Treatment 1 will be a 5 hour hemodialysis treatment session utilizing heparin anticoagulation. The first hour will utilize a blood flow rate (BFR) of 300 mL/min and a dialysate flow rate (DFR) of 600 mL/min with no ultrafiltration (UF). After the first hour, the blood flow rate will be adjusted to 200 mL/min with a dialysate flow rate of 400 mL/min. This BFR and DFR will be maintained for the remaining 4 hours of the 5 hour session.

Treatment 2 will be a 5 hour hemodialysis treatment session. The first hour will be undertaken with heparin anticoagulation utilizing a BFR of 300 mL/min and a dialysate flow rate of 600 mL/min with no UF. After the first hour, the SCD will be integrated into the circuit with regional citrate anticoagulation and BFR adjusted to 200 mL/min with a DFR of 400 mL/min. This BFR and DFR with RCA will be maintained for the last 4 hours of the 5 hour session.

Of importance, this 5 hour session is planned to ensure adequate solute clearance but with only 4 hour high UF to achieve the patients dry weight.

The hemodialysis treatments will be performed at the Acute Dialysis Unit, University of Michigan.

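### Section 9 analyses a peak frequency of stunning that the scheduled echoes cannot supply, and the post-session echo of this transient outcome has no stated time window

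*Combined protocol and SAP*

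**What the plan says.** Section 9 names regional wall abnormalities as the primary outcome and gives the test: "Independent t-test will be used to compare the peak frequency of MS between SHH and SCD sessions". The next sentence plans a repeated-measures comparison of "Global LVEF and wall motion in 16 segments in 8 regions at each time point in the dialysis session".

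The procedures in section 8.3.1 list three echoes per treatment: 8.3.1.1 (before), 8.3.1.38 (after) and 8.3.1.40 (24 hours). They apply to both treatments, since "identical study procedures will be performed during each study treatment". Section 8.4.1 agrees on the three scans: "Scores from pre HD, post HD and 24 hour post HD Echos from all 10 patients will be collated".

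The contrast is described differently elsewhere. Section 4.1 says "Regional myocardial wall abnormalities and biomarker measurements will be compared pre and post hemodialysis", and section 8.4.1 says "Each patient will therefore serve as his or her own control comparing pre-and post-dialysis echocardiograms", with the standard session set against the SCD session.

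On how long the finding lasts, the myocardial stunning part of section 1 says "The majority of these areas of MS improve within 30 minutes post hemodialysis".

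**The concern.** There are two linked problems, both affecting the primary outcome.

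First, section 9 presupposes observations during dialysis that nobody will make. With no definition of peak frequency, the analyst has to choose the statistic for a ten-patient trial, possibly after seeing the data. The natural candidates are not equivalent.

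Second, the outcome fades. If most stunned areas improve within half an hour, the time at which the post scan is taken partly determines what it shows. The two sessions also end differently. Only the SCD session involves returning blood from the SCD system (6.3.9), a saline flush and elution-buffer step (6.3.10) and a five-hour ionized calcium (8.3.1.31). If such steps delay the scan more in one session than in the other, the delay is confounded with treatment.

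**Working it through.** **1. Echo count.** Scans per treatment: 8.3.1.1 + 8.3.1.38 + 8.3.1.40 = 3. The echo row of Appendix 1 also carries three marks. The steps listed for hours 1 to 4 (8.3.1.22 to 8.3.1.26) contain no echo, and neither do the in-treatment procedures (8.3.1.18 to 8.3.1.21). Scans during the five-hour session = 0, so at most one scan, the post echo, falls close to the dialysis-induced event. A peak needs at least two observations over the period in which it is sought.

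**2. What peak could mean on three scans.** At least two readings are computable: (a) the worst of the pre, post and 24-hour values; (b) the larger of the post and 24-hour changes from the pre value. The word frequency adds a further choice, between a count of affected segments or regions and the mean score in section 8.4.1. The protocol does not choose.

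**3. Tolerances stated in Appendix 1.**

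| Item | Tolerance |
|---|---|
| Ionized calcium, CBC, metabolic panel (note 6) | 15 minutes |
| Vital signs (note 5) | 20 minutes |
| Baseline echo to start of dialysis (note 1) | 2 hours |
| 24-hour visit (column heading) | ± 4 hours |
| Post-session echo | none stated |

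The column positions in Appendix 1 are broken in the text available here. The middle echo mark appears to sit at 5 hours. Even so, that is a nominal time, because notes 5 and 6 do not cover echo.

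**4. Place in the sequence.** Section 8.3.1 lists the post echo after 8.3.1.32, 8.3.1.33, either 8.3.1.34 or 8.3.1.35, 8.3.1.36 and 8.3.1.37. That is at most five steps for any one patient, the last being circuit disassembly. List order does not prove elapsed time, but nothing in the text limits it. The one-hour observation in 8.3.1.39 is a minimum stay, not an echo window.

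**5. The plan's own figure.** Section 9 gives N = 10 for a difference of 20%, SD 14%, alpha 0.05 and 80% power. Two-group normal approximation, two-sided: n = 2 × [14 × (1.960 + 0.842) / 20]² = 7.7, so 8 per condition. The exact independent t-test needs 9 per condition, and power at 10 per condition is 86%. If 14% is instead the SD of the within-patient difference, a paired t-test needs 7 patients, with 98% power at 10. So N = 10 is not challenged on the stated inputs. The documents do not say which wall-motion measure the 20% and 14% refer to, or whether 14% is a between-patient or within-patient SD. The redefined outcome must be matched to them.

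**The case against.** Several points on the other side have force. Section 8.4.1 already commits to comparing pre, post and 24-hour scores between treatments, so the mention of session time points in section 9 can be read as loose wording for those scans. The synopsis calls the primary analyses descriptive, and section 4.1 calls the trial an exploratory pilot. The echo parameters are "as noted on the echocardiographic case report form", and that form, which may record scan times, is not among the documents. The 30-minute statement speaks of improvement, not resolution, and rests on cited studies.

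These points limit the concern but do not remove it. Sections 8.4.1 and 9 both plan significance testing, a descriptive summary also needs a defined quantity, and a recorded time is not a window.

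A reader might infer that peak must mean the worst of the three scans, and that this would discard about half of the treatment effect. The documents do not support that. Suppose, as an assumption, independent scan noise with SD 1, only the post scan shifted, and an SCD effect that abolishes the shift. At a shift of 1 SD, the worst of three keeps 48% of the difference, but the larger of the two changes keeps 64%. Raw retention also misleads. The standardised between-session effect is 0.44 for worst-of-three against 0.50 for the pre-to-post change at 1 SD, but 1.06 against 1.00 at 2 SD and 1.76 against 1.50 at 3 SD. The pre-to-post change is preferable because it is defined and matches the design, not because it is always more sensitive.

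A reader might also infer that the post echo will be late, or later after SCD. Neither is shown: some closing steps may run in parallel.

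**Conclusion.** The concern holds as a mismatch that should be fixed. Section 9 names an analysis that the echo schedule cannot deliver, leaves its key term undefined, and departs from the contrast in sections 4.1 and 8.4.1. This rests on the numbered procedures and does not depend on the broken table.

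The missing post-echo tolerance is a risk, not a demonstrated bias. Its size and direction cannot be derived, because the documents quantify neither the recovery beyond a majority within 30 minutes nor the likely delay in either session. No loss of effect or power is claimed for either part. The timing part assumes that neither the echo case report form nor the two figures in section 4.1 that are not shown sets a window.

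**What to change.** 1. In section 9, replace the peak-frequency outcome with the within-patient change from the same-day pre echo to the post echo in one named measure. Examples are the global wall motion score of section 8.4.1 or the number of segments that worsen. Match it to the measure behind the 20% difference and 14% SD. Compare treatments with a paired analysis in place of the independent t-test, since each patient is his or her own control. Replace the reference to time points within the session by pre, post and 24 hours.

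2. State one post-session echo window, the same for both treatments. Wall-motion image acquisition should start as soon as feasible and within 30 minutes of a defined end of dialysis, with the exact minutes set by the sponsor.

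3. Make 8.3.1.38 and Appendix 1 agree on when the scan is done, so that it need not wait for circuit disassembly.

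4. Record the time from end of dialysis to echo in both sessions, if the case report form does not already do so, and report it by treatment. Section 6.3.13 already requires the time at which SCD therapy stops; the text has no matching line for Treatment 1.

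Cost: wording in three places and at most one new time field. The scans stay at three per treatment. The downside is slightly tighter sonographer logistics at the end of each session.

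### Section 9's 80% power covers one unadjusted comparison, but the plan tests wall motion in several ways, one with an undefined Bonferroni family, and does not say which test the power belongs to.

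*Combined protocol and SAP*

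**What the plan says.** The relevant text is in Section 9 (Statistical Considerations) and Section 8.4.1 (Echocardiographic Methods).

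- **Sample size.** Section 9 opens with "Sample size determination for primary outcome regional wall abnormalities". It continues: "Sample size of 10 would appear to be sufficient to detect a difference of 20% and is based upon a standard deviation of 14" percent, with "significance level of 0.05 and 80% power". Sidedness and dropout are not stated, nor is the scale of the 20% and 14%, nor whether the SD is per session or that of the within-patient difference.
- **Design.** "The patients will serve as their own controls, comparing BL-SHH parameters to SCD therapy parameters". The data are therefore paired.
- **First wall-motion test.** "Independent t-test will be used to compare the peak frequency of MS between SHH and SCD sessions".
- **Second wall-motion test.** Global LVEF is handled in the same sentence, and "wall motion in 16 segments in 8 regions at each time point in the dialysis session will be compared using repeated measures". The method is given as "compared using repeated measures and Bonferroni's test for multiple comparisons". The number of comparisons covered is not stated.
- **Third wall-motion test.** In Section 8.4.1, "Scores will be tabulated for each of 16 predefined segments", each on a 1 to 4 scale, and averaged over the visualized segments into a global wall motion score. Scores from three echocardiograms per treatment (before, after, and 24 hours after dialysis) are to be tested for a difference between treatments.

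The Synopsis, under Primary Analyses, describes these analyses as descriptive. Section 4.1 calls the study an exploratory pilot.

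**The concern.** A power statement applies to a particular endpoint, test and significance level. Here there is one power statement and three candidate tests of the outcome called primary. One of the three is adjusted for multiplicity over a family of unstated size, whereas the sample size was worked out at the full 0.05.

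Two things are at stake. The primary result could be taken from any of the three tests after the data are seen. And a reader who meets non-significant segment results beside a claim of 80% power could take them as evidence against an effect of the planned size, when those tests may have had much lower power.

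**Working it through.** **Inputs.** From Section 9: N = 10, difference 20, SD 14, alpha 0.05, power 80%. From Section 8.4.1: 16 segments, 3 echo times per treatment. Assumed: two-sided tests, no dropout.

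**Step 1: reproduce the plan's figure.** For a single independent comparison by normal approximation, n per session = 2 × (1.96 + 0.84)² × 14² / 20² = 7.7, so 8. The t-test needs 9. At 10 per session:

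- Independent t-test: noncentrality 20 / (14 × √(2/10)) = 3.19, 18 df, critical value 2.10, power 85.5%.
- Paired t-test, reading 14 as the per-session SD with zero correlation: SD of the difference 14 × √2 = 19.8, noncentrality 20 / (19.8/√10) = 3.19, 9 df, critical value 2.26, power 81.1%.
- Paired t-test, reading 14 as the SD of the difference: noncentrality 20 / (14/√10) = 4.52, power 97.9%.

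The stated 80% is therefore supported for one unadjusted comparison.

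**Step 2: apply Bonferroni.** Keep N = 10 and replace alpha by 0.05/m. For within-patient correlation ρ, the SD of the difference is 14 × √(2(1 − ρ)): 19.8 at ρ = 0, 14.0 at 0.5, 12.5 at 0.6 and 10.8 at 0.7. Applying 20 and 14 to a single segment, region or time point is an assumption, so these figures are illustrative. Power is per comparison.

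| Family | m | Alpha | Independent t | Paired, ρ = 0 | Paired, ρ = 0.5 |
|---|---|---|---|---|---|
| None | 1 | 0.05 | 85.5% | 81.1% | 97.9% |
| Time points | 3 | 0.0167 | 70.7% | 61.4% | 91.4% |
| Regions | 8 | 0.00625 | 55.1% | 42.6% | 79.6% |
| Segments | 16 | 0.003125 | 44.3% | 30.9% | 68.1% |
| Segments × times | 48 | 0.00104 | 29.2% | 16.9% | 47.9% |

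Example for m = 16, ρ = 0: the critical value on 9 df rises from 2.26 to 4.00 while the noncentrality stays at 3.19, which gives 30.9%.

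**Step 3: higher correlation.** At m = 16, paired power is 80% at ρ = 0.6 and 92% at ρ = 0.7. At m = 48 and ρ = 0.7 it is 79%.

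**Step 4: chance that at least one segment is significant.** Paired tests at 0.05/16 with N = 10 were simulated with the effect in 4 or in all 16 segments, SD of differences 14 or 19.8, and between-segment correlation from 0 to 0.8. The chance of at least one significant segment ran from about 52% (4 segments, SD 19.8, correlation 0.8) to nearly 100%.

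**The case against.** The strongest reply is that Section 9 never attaches the 80% to the segment analysis. The single t-test on peak stunning frequency comes first, and the stated N fits it. On that view the calculation contains no error. This stands: a reader might infer that the stated power is wrong, and the documents do not support that. What they show is that the power figure is not assigned to any one test.

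The second reply is that the Bonferroni family is unknown. It could be three time points, in which case a paired test with SD of differences 14 keeps 91%. This also stands, and it is why the loss is given as a range.

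A reader might further infer that the segment analysis would probably be negative or could not succeed with 10 patients. Steps 3 and 4 contradict this: per-segment power reaches 80% or more at correlations of 0.6 to 0.7, and the chance of some significant segment was above one half in every case simulated.

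It is also tempting to argue from an exact test on segments classed as worsened or not, where only 10 of 10 patients changing the same way would pass 0.05/16. The plan specifies neither that test nor that dichotomy for segments, so the argument does not bear on the planned analysis.

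Finally, the study is a small pilot with descriptive primary analyses in the Synopsis, and Section 8.4.1 already defines a per-patient score. That lowers the stakes and makes the remedy easy. It does not remove the gap, because Section 9 still makes a formal power claim and plans formal tests.

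**Conclusion.** The point holds as a gap in specification. Section 9 powers its primary outcome for one comparison at an unadjusted 0.05 but does not say which of three wall-motion analyses that comparison is. The 80% makes no allowance for the Bonferroni adjustment planned for one of them.

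On the assumption that the 20% and 14% apply to each comparison, with a paired two-sided test, N = 10 and within-patient correlation 0 to 0.5, power per comparison would be about 31% to 68% over 16 segments, 43% to 80% over 8 regions, and 61% to 91% over 3 time points. The documents give neither the correlation nor the family, so no single figure can be defended. Non-significant segment results should not be judged against 80% power.

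**What to change.** In Section 9:

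1. Name one per-patient wall-motion summary as primary. The change in global wall motion score is already defined in Section 8.4.1; the number of segments worsened by at least one grade is an alternative.
2. Compare it once between the two sessions, within patient (paired), at two-sided 0.05.
3. State that the 80% power refers only to this test, and give the SD of the within-patient difference it assumes, on the scale of the chosen summary.
4. Report segment and region results descriptively.
5. Bring the Synopsis wording on primary analyses into line.

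This needs a change of wording only, with no added patients, visits or echocardiograms. The cost is the formal segment-level tests. If the sponsor wants to keep those, the alternative is to define the Bonferroni family and restate the power at the adjusted level. At 0.05/16 with the same inputs, 80% power needs 12 patients (paired, SD of differences 14) or 17 per session (independent).
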